15.3.3.2 Listing of Secondary Biomarkers and Sampling / Collection Times

12.6.2.1.1 Confirmatory Analysis

The hypothesis to be tested for each of the secondary BoExp is that the geometric mean level on Day 5 of the BoExp for THS 2.2 is lower relative to CC.

Analysis of the secondary BoExp will be conducted on the natural log scale. In order to test the follow hypothesis

$$\begin{aligned} \text{Null hypothesis (H}_0\text{):} & \quad m_1 \geq m_2 \\ \text{Alternative hypothesis (H}_1\text{):} & \quad m_1 < m_2 \end{aligned}$$

Where m_1 and m_2 are the geometric means of the BoExp levels on Day 5 for THS 2.2 and CC respectively.

The SAS code will be the same as described in Section 12.6.1.1 “Primary Biomarkers of Exposure in 24 hour collection”.

12.6.2.2 Nicotine and Cotinine Concentrations

The change from the Day 0 sample will be calculated for the Day 5 sample closest to 08:00 PM only. The concentrations of nicotine and cotinine will be listed and summarized along with this change. Line graphs of the nicotine and cotinine concentration profiles across all study days showing mean and 95% CI will also be produced.

For nicotine and cotinine plasma concentrations the change from baseline (Day 0 sample at 08:00 PM - 09:30 PM) on the Day 5 sample closest to 08:00 PM will be analyzed using an ANCOVA model with terms for baseline (Day 0) concentration, sex, average daily CC consumption over the last 4 weeks as reported during screening and product. No adjustment will be made for multiple comparisons.

The SAS code to be used is shown below:

```
Proc mixed data=_data_ ;  
Class product sex cigarette_cons time_point ;  
Model change from baseline = baseline sex cigarette_cons product ;  
Lsmean product / diff alpha=0.05 cl ;  
Run ;
```

LS means for each product along with the difference (THS 2.2 - CC) and 95% CI will be presented in the tables.

All figures, summaries and analyses will be performed on the FAS only.

The data will be presented in the below outputs, the TFL number refers to the TFL number in the accompanying TFL shell document:

TFL number	Title
FIGURES	
15.1.2.31	Plasma Nicotine Concentrations (ng/mL) Mean and 95% CI on Day 5 – FAS
15.1.2.32	Plasma Cotinine Concentrations (ng/mL) Mean and 95% CI on Day 5 – FAS
TABLES	
15.2.4.40	Descriptive Statistics of Plasma Nicotine Concentrations (ng/mL) – FAS
15.2.4.41	Descriptive Statistics of Plasma Cotinine Concentrations (ng/mL) – FAS
15.2.4.46	Analysis of Change from Day 0 Plasma Nicotine and Cotinine Concentrations at 08:00 PM on Day 5 – FAS
LISTINGS	
15.3.3.4	Listing of Plasma Nicotine Concentrations and Sampling Times
15.3.3.5	Listing of Plasma Cotinine Concentrations and Sampling Times

12.6.2.3 Nicotine and Cotinine Pharmacokinetic Parameters

The parameters C_{peak} , C_{avg} and t_{peak} will be determined on Day 5 as described in Section 7.2 “**Pharmacokinetic Parameters**”. The data will be listed and summarized for both nicotine and cotinine.

The analysis will compare C_{peak} and C_{avg} on Day 5 between the THS 2.2 and CC arms. An analysis of variance (ANOVA) model will be used with terms for sex, average daily CC consumption over the last 4 weeks as reported during screening and product. No adjustment will be made for multiple comparisons.

The SAS code will be similar to that described in Section 12.6.1.1 “**Primary Biomarkers of Exposure in 24 hour collection**”, with no baseline value being included in the model.

LS means for each product along with the difference (THS 2.2 - CC) and 95% CI will be presented in the tables.

For t_{peak} on Day 5 the comparison between the THS 2.2 and CC arms will be made by the Wilcoxon Rank Sum test using PROC NPAR1WAY in SAS.

The data will be presented in the below outputs, the TFL number refers to the TFL number in the accompanying TFL shell document:

TFL number	Title
TABLES	
15.2.4.42	Descriptive Statistics of Plasma Nicotine Concentration Parameters on Day 5 – FAS
15.2.4.43	Descriptive Statistics of Plasma Cotinine Concentration Parameters on Day 5 – FAS

TFL number	Title
15.2.4.44	Analysis of Plasma Nicotine Concentration Parameters on Day 5 – FAS
15.2.4.45	Analysis of Plasma Cotinine Concentration Parameters on Day 5 – FAS
LISTINGS	
15.3.3.6	Listing of Plasma Nicotine Concentration Parameters on Day 5
15.3.3.7	Listing of Plasma Cotinine Concentration Parameters on Day 5

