- THS 2.2 Arm: 80 subjects, *ad libitum* use of the product.
- CC Arm: 40 subjects, *ad libitum* use of their preferred CC brand.
- SA Arm: 40 subjects who will abstain from smoking.
Subjects will be informed of their randomized study arm by the study site collaborator on Day 1 prior to 06:30 AM.

- Exposure period (from Day 1, 06:30 AM until Day 5, 11:00 PM):
The exposure period will consist of 5 days of *ad libitum* use of the assigned product between 06:30 AM and 11:00 PM in THS 2.2 and CC arms. Use of any tobacco/nicotine containing product other than the assigned product will not be allowed and may, at the discretion of the Investigator, result in the subject withdrawal from the study.

Subjects in the SA arm will be asked to abstain from smoking any nicotine/tobacco containing product and will not be provided with medication to support SA. Subjects will be provided with psychological support during the period of smoking abstinence.

The end of the 24-h urine collection period for Day 5 will end in the morning on Day 6 prior to Discharge.

- Day of Discharge (Day 6) (from Day 5, 11:01 PM to time of Discharge):
Procedures of Discharge, including but not limited to laboratory parameters, will be conducted to discharge the subject from the clinic after 9 days in a confined setting. Use of CC will be allowed on Day 6, but only after spirometry has been performed.
- Safety follow-up period (from the time of Discharge on Day 6 to Day 13):
After time of Discharge, subject will enter a 7-day safety follow-up during which there will be recording of spontaneously reported new AEs/SAEs and the active follow-up of ongoing AEs/SAEs by the study site. In general, all AEs will be followed until resolved, stabilized (i.e., no worsening of the event), or a plausible explanation for the event has been found. The end of the study is defined as the time of Discharge on Day 6 plus 7-day follow-up period.

During the study, any subjects who want to quit smoking will be encouraged to do so, and will be referred to medical services and will be withdrawn from the study. This is applicable for all subjects during screening to the baseline period and for subjects allocated to THS 2.2 or CC arms during the exposure period.

Study Population and Main Criteria for Inclusion and Exclusion:

160 female or male smoking, healthy Japanese adult subjects meeting the following main inclusion criteria:

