7.5.1.2 Plasma Nicotine and Cotinine

Nicotine and cotinine concentrations will be measured in plasma to evaluate the exposure to nicotine. For subjects in the SA arm, blood samples will be collected on Days 0 to 4, at comparable time points. No nicotine PK profile will be done for subjects in the SA arm on Day 5 and Day 6.

- On Day 0 to Day 4 (all study arms):

One blood sample for nicotine and cotinine will be drawn each day between 08:00 PM-09:30 PM.

- Nicotine/cotinine PK Profile on Day 5 and Day 6 (THS 2.2 and CC arms only):

In total, 9 blood samples will be drawn on Day 5. The first blood sample on Day 5 will be drawn within 15 minutes prior to the first product use (=T0). On Day 5, T0 will serve as a

Confidentiality statement: Data and information contained in this document are considered to constitute trade secrets and confidential commercial information, and the legal protections provided to such trade secrets and confidential information are hereby claimed under the provisions of applicable law. No part of this document may be publicly disclosed without the written consent of Philip Morris Products S.A.

reference for the time to peak concentration. An additional 8 blood samples will be drawn in 2-hour intervals after T₀. The last blood sample should be drawn no later than 11:00 PM, corresponding to the end of the product use period. At all time-points, if the subject wants to smoke around the time of the blood draw, he/she should smoke first and the blood will be drawn after the product has been used. Depending on the time of the first product use, it may be that fewer than 8 blood samples will be collected from a subject after T₀.

On Day 6, two blood samples will be drawn. The first one will be 20 hours after T₀ and the second blood sample will be 24 hours after T₀ (with T₀ being the time of the first product use on Day 5).

- On Day 5 and Day 6 (SA arm only):

On Day 5, one blood sample will be drawn between 08:00 PM-09:30 PM.

On Day 6, one blood sample will be drawn between 08:00 AM-09:30 AM.

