12.4.4 Confirmatory Analysis

The hypothesis to be tested for each of the primary and secondary biomarkers of exposure is that the geometric mean level on Day 5 of the biomarker for THS 2.2 is lower relative to CC.

Analysis of BoExp will be conducted on the natural log scale. In order to test the following hypothesis

Null hypothesis (H0): $m_1 \geq m_2$

Alternative hypothesis (H1): $m_1 < m_2$

Where m_1 and m_2 are the geometric means of the biomarker levels on Day 5 for THS 2.2 and CC respectively.

The transformed data will be analyzed by means of a generalized linear model using product arm as covariate adjusting for the following baseline information: sex, average cigarette

consumption over the previous 4 weeks, and baseline value of endpoint. Estimates of differences between groups will be back-transformed to provide relative effects.

Assumptions of the analysis of variance model will be tested. Markedly non-lognormally distributed BoExp data will be transformed or analyzed by appropriate non-parametric methods.

Should more than 20% of the subjects be excluded from the FAS, would the above confirmatory analysis will be repeated on the PP population.

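### Day 5 nicotine and cotinine Cpeak and Cavg are compared without the Day 0 concentration that the plan already collects, which gives up precision but causes no bias

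*SAP*

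**What the plan says.** For Cpeak and Cavg, SAP 12.6.2.3 states: "An analysis of variance (ANOVA) model will be used with terms for sex, average daily CC consumption over the last 4 weeks", plus product. It takes its code from SAP 12.6.1.1 "with no baseline value being included in the model". No reason is given.

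Protocol 7.5.1.2 provides, for Day 0 to Day 4 and all arms: "One blood sample for nicotine and cotinine will be drawn each day between 08:00 PM-09:30 PM". Table 9 of the Protocol repeats this sample for Day 0. All subjects smoke their own cigarettes until Day 1 and learn their arm that morning before 06:30 AM (Protocol 4.1 and 6.3).

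SAP 12.6.2.2 analyses the change from Day 0 to the Day 5 sample closest to 08:00 PM by an "ANCOVA model with terms for baseline (Day 0) concentration, sex, average daily CC consumption over the last 4 weeks" and product. In the THS 2.2 and CC arms, that Day 5 sample belongs to the series from which Cpeak and Cavg are derived (Protocol 7.5.1.2, SAP 7.2).

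**The concern.** The SAP adjusts one point of the Day 5 profile for the subject's Day 0 concentration but does not adjust the summaries of the whole profile. A covariate need not be the same measure as the outcome. It has to be unaffected by assignment, and it helps if it predicts the outcome. The Day 0 value meets the first condition and plausibly the second, since the same person's intake and clearance lie behind both measurements.

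Cigarette consumption covers this only in part. It enters as a class variable, with strata of 10 to 19 and more than 19 per day (SAP 7.5), so differences within a stratum remain.

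At stake is the width of the interval for the THS 2.2 versus CC comparison. The sample may also be smaller than 120: SAP 7.2 requires every sample to be present, while Protocol 7.5.1.2 accepts that some subjects will have fewer than eight samples after T0. Eight two-hour steps take 16 hours, so finishing by 11:00 PM needs a first product use by 07:00 AM. How many subjects this would remove is not stated.

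**Working it through.** The documents give no power or precision for Cpeak or Cavg, so there is no figure to reproduce.

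**Inputs**
- Arm sizes: "THS 2.2 Arm: 80 subjects" and 40 in CC (Protocol synopsis). The SA arm has no PK profile (Protocol 7.5.1.2), so the model holds at most 120 subjects.
- Two-sided 95% CI (Protocol 12.1.5).
- Model: intercept, product, sex and consumption use 4 degrees of freedom, leaving 116, or 115 with the covariate.
- rho: correlation of the Day 0 concentration with the Day 5 parameter after sex and consumption. It is not in the documents and is assumed at 0, 0.3, 0.5 and 0.7.

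**Formulas** (in units of the residual SD of the present model)
- Without baseline: half-width = t(0.975; 116) × √(1/80 + 1/40) = 1.981 × 0.1936 = 0.3835.
- With baseline: half-width = t(0.975; 115) × √(1/80 + 1/40) × √(1 − rho²) × √(1 + 1/114). The last factor allows for chance imbalance in the covariate.
- Equivalent sample size without baseline = 120 / (1 − rho²).
- Difference detectable with 80% power, one-sided 2.5% = (1.960 + 0.842) × 0.1936 × √(1 − rho²), which is 0.543 SD at rho = 0.

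| rho | half-width (SD) | ratio to 0.3835 | detectable difference (SD) | equivalent N |
|---|---|---|---|---|
| 0 | 0.3853 | 1.004 | 0.543 | 120 |
| 0.3 | 0.3675 | 0.958 | 0.518 | 132 |
| 0.5 | 0.3336 | 0.870 | 0.470 | 160 |
| 0.7 | 0.2751 | 0.717 | 0.387 | 235 |

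The two half-widths are equal at rho of about 0.09. A simulation of 3,000 trials per value gave width ratios of 1.004, 0.958, 0.869 and 0.716, in agreement with the formula.

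**The case against.** The strongest defence is that no baseline of this endpoint exists. The profile is drawn only on Days 5 and 6, so there is no Day 0 Cpeak or Cavg. This is true, and it disposes of one stronger reading, that the SAP departs from the Protocol. Protocol 12.4.4 adjusts for "consumption over the previous 4 weeks, and baseline value of endpoint", but it does so in the primary confirmatory section, and Protocol 12.5 specifies only descriptive summaries for secondary endpoints. There was no Protocol model for the PK parameters to depart from. It does not follow that a different measure from the same analyte should be left out.

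A second defence is that the objective is only to describe the PK profiles (Protocol 3.2). A reader might infer that the comparison supports a claim of similar nicotine delivery. The documents attach no similarity hypothesis, margin or success rule to Cpeak or Cavg; similar nicotine kinetics appear only as background on the predecessor product (Protocol 2.1.2). Baseline-adjusted comparisons of plasma nicotine and cotinine at one time point and of urinary nicotine equivalents are also planned (SAP 12.6.2.2 and 12.6.2.1). This limits the importance of the point.

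A third defence is that the correlation may be weak, especially for nicotine:
- On Day 5, a subject who wants to smoke does so before the draw; on other days procedures take priority (Protocol 6.6.1).
- Smoking on Day 0 goes through the topography device where one is assigned and compatible; Day 5 has no topography (Protocol 7.8.1).
- In the THS 2.2 arm the product changes between the two days.

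These are fair reasons to expect less gain for nicotine than for cotinine. They are why the range must start at zero. They are not reasons to omit the term, since the worst case costs 0.4% in width.

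**Conclusion.** The point stands as a loss of precision of unknown size in a secondary analysis, and it is minor. With 80 against 40 subjects and no losses, including the Day 0 concentration changes the CI width by between +0.4% (rho 0) and −28% (rho 0.7), and it gains for any rho above about 0.09. These figures rest on an assumed rho and a linear model.

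Three stronger readings are not supported:
- **Bias.** The comparison is randomised, stratified on sex and consumption, and includes both terms. The unadjusted interval already allows for chance imbalance.
- **A gain of 40% in width, or 2.8 times the sample size.** This needs rho = 0.8, since √(1 − 0.64) = 0.60 and 1/(1 − 0.64) = 2.78. Nothing in the documents supports that value, least of all after sex and consumption are in the model.
- **A covariate that is strictly pre-randomisation.** Randomisation may take place at any time on Day 0 (Protocol 6.3). The evening sample is certain only to precede disclosure of the arm and first assigned use, which is enough for it to serve as a covariate.

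**What to change.** In SAP 12.6.2.3, add the Day 0 08:00 to 09:30 PM concentration of the same analyte as a covariate in the Cpeak and Cavg models, on the same scale as the outcome. Say that it is a single-time concentration and not a baseline Cpeak or Cavg. SAP 12.1.5 does not impute missing data, so state how a subject without a Day 0 value is handled. The Wilcoxon comparison of time to peak is unaffected.

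The cost is one model term and one degree of freedom. The samples are already scheduled, and SAP section 3 allows amendment until database lock.

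Separately, reconcile the scale in the same section. The code it refers to models log values and leads to a ratio in SAP 12.6.1.1, while SAP 12.6.2.3 reports a THS 2.2 minus CC difference. The scale should be stated, but moving to logs and a ratio does not follow from the baseline point.

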12.6.2.4 CYP1A2 Activity

CYP1A2 activity will be measured in plasma on Day 0 and Day 5. In this study the CYP1A2 activity will be calculated using the molar ratio of PX and CAF, as described in Section 7.1.4 “CYP1A2”. Descriptive statistics of the values and percent change on Day 5 from Day 0 and supportive listings will be provided.

The analysis will compare the Day 5 values between the THS 2.2 and CC arms and between the THS 2.2 and SA arms. An ANOVA model will be used with terms for sex, average daily CC consumption over the last 4 weeks as reported during screening and product. No adjustment will be made for multiple comparisons.

The SAS code will be the same as described in Section 12.6.1.1 “Primary Biomarkers of Exposure in 24 hour collection”, with no baseline value being included in the model.

LS means for each product along with the difference (THS 2.2 - CC) and 95% CI will be presented in the tables.

CYP1A2 activity will also be examined to compare the observed reductions in THS 2.2 vs. SA using the same methodology as above.

The data will be presented in the below outputs, the TFL number refers to the TFL number in the accompanying TFL shell document:

TFL number	Title
TABLES	
15.2.4.54	Descriptive Statistics of CYP1A2 Activity (%) – FAS
15.2.4.55	Analysis of CYP1A2 Activity (%) on Day 5– FAS
LISTINGS	
15.3.4.1	Listing of CYP1A2 Activity and Changes from Baseline

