7.5.2.2 CYP1A2 activity test

CYP1A2 activity will be measured at Day 0, and at Day 5. Measurement of enzyme activity will be assessed through paraxanthine (PX) and caffeine (CAF) plasma molar concentrations approximately 6 hours (± 15 minutes) after the intake of one Tomerumin® (LionCorp.) caffeine tablet (around 170 mg caffeine) with 150 ml ± 10 ml water (Faber and Fuhr, 2004).

The exact time of intake of the caffeine tablet in the morning and of the blood sampling (blood sample will be taken 6 hours [± 15 minutes] after the intake of the caffeine tablet) must be recorded. Cytochrome P450 1A2 activity will be assessed by the measurement of the molar PX/CAF metabolic ratio (Faber and Fuhr, 2004).

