	√	CYP2A6 activity in plasma	To be done prior to smoking.
		Assessment of cough (VAS)	To be done prior to smoking but not later than 10:00 AM.
		MNWS questionnaire	To be done prior to smoking but not later than 10:00 AM .
		Spirometry without short-acting bronchodilator	To be done prior to smoking
		CO breath test	To be done within 15 minutes prior to smoking
		HST	HST SODIM® device has to be used for all product uses if compatible CCs are smoked
06:30 AM		Beginning of smoking period	
	√	Clinical laboratory parameters (hematology, clinical chemistry)	In at least 10 hours of fasted condition
	√	Bio-banking for transcriptomics (if consent is obtained)	In at least 10 hours of fasted condition .
	√	Bio-banking for BoExp/ risk markers in serum/plasma (if consent is obtained)	In at least 10 hours of fasted condition
		Urine safety analysis	
Before 10:00 AM		Breakfast	

Confidentiality statement: Data and information contained in this document are considered to constitute trade secrets and confidential commercial information, and the legal protections provided to such trade secrets and confidential information are hereby claimed under the provisions of applicable law. No part of this document may be publicly disclosed without the written consent of Philip Morris Products S.A.

Time	Blood sample	Procedures	Additional information
Start of procedure		Baseline Day 0	
10:00 AM-11:30 AM		Vital signs (blood pressure, pulse rate, respiratory rate)	At least 5 minutes in supine position prior to measurement
10:00 AM-11:30 AM		A caffeine tablet containing around 170 mg of CAF with 150 ± 10mL water	
12:00 PM-01:30 PM		CO breath test	
Before 02:30 PM		Lunch	
04:00 PM-05:30 PM	√	CYP1A2 activity in plasma	6 hours +/-15minutes after intake of caffeine tablet
04:00 PM-05:30 PM		CO breath test	
Afternoon		Snacks	
In the evening until 09:00 PM		Dinner	
08:00 PM-09:30 PM		CO breath test	
08:00 PM-09:30 PM	√	COHb in blood	
08:00 PM-09:30 PM	√	Nicotine, cotinine in plasma	
08:00 PM-09:30 PM		HST questionnaire	
08:00 PM-11:00 PM		MCEQ questionnaire, QSU-brief questionnaire	
11:00 PM		End of smoking period	

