12.6.1 Primary Analyses

12.6.1.1 Primary Biomarkers of Exposure in 24 hour collection

The primary BoExp (COHb in blood and urinary concentrations adjusted for creatinine of MHBMA, 3-HPMA and S-PMA) will be summarized as detailed in Section 12.1.3 “Descriptive Statistics”.

The baseline is as defined in Section 12.1.4 “Definitions for Statistical Data Analysis”,

The values and percent changes in the concentration adjusted for creatinine will be listed and summarized along with the COHb concentrations and percent changes from baseline. In addition line graphs will be produced for means (and 95% CI) over all timepoints.

For all arms the 24 hour urine collection will be collected daily from Day -1 to Day 5. Although the 24 hour urine collection will span into the following Day it will be reported by the day the collection started.

The primary endpoints will be log-transformed (base_e) prior to analysis. The analysis will compare (1) last Day 5 values of COHb in blood and (2) urinary concentrations of MHBMA, 3-HPMA and S-PMA corrected for creatinine on Day 5 between the THS 2.2 and CC arms. An ANCOVA (Snedecor and Cochran 1982) model will be used with terms for the log-transformed baseline value, sex, average daily CC consumption over the last 4 weeks as reported during screening and product.

The SAS code to be used is shown below:

```
Proc mixed data=_data_ ;
Class product sex cigarette_cons ;
Model log (Day 5) = log (baseline) sex cigarette_cons product ;
Lsmean product / pdiff =control('CC') alpha=0.05 cl ;
Run ;
```

The least squares (LS) means and estimate of the difference along with it's 95% CI will be back-transformed before presenting in the tables. The geometric LS means for each product along with the ratio (THS 2.2 : CC) and 95% CI will be presented in the tables.

In addition line graphs will be produced for product means (and 95% CI) over all timepoints for COHb in blood and urinary concentrations adjusted for creatinine of MHBMA, 3-HPMA and S-PMA.

The data will be presented in the below outputs, the TFL number refers to the TFL number in the accompanying TFL shell document:

TFL number	Title
FIGURES	
15.1.1.1	Blood COHb (%) Mean and 95% CI– FAS
15.1.1.2	MHBMA Urinary Concentration Adjusted for Creatinine (units) Mean and 95% CI – FAS
15.1.1.3	3-HPMA Urinary Concentration Adjusted for Creatinine (units) Mean and 95% CI– FAS
15.1.1.4	S-PMA Urinary Concentration Adjusted for Creatinine (units) Mean and 95% CI– FAS

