The last measurement of exhaled CO will be used in the analysis. An ANCOVA model will be used with terms for the baseline value, sex, average daily CC consumption over the last 4 weeks as reported during screening and product. No adjustment will be made for multiple comparisons.

The analysis will compare the log-transformed urinary concentrations corrected for creatinine on Day 5 to 6 and the quantity excreted over 24-hours on Day 5 to 6 between the THS 2.2 and CC arms. An ANCOVA model will be used with terms for the log-transformed baseline value, sex, average daily CC consumption over the last 4 weeks as reported during screening and product. No adjustment will be made for multiple comparisons.

The SAS code will be the same as described in Section 12.6.1.1 “**Primary Biomarkers of Exposure in 24 hour collection**”.

LS means for each product along with the difference (THS 2.2 - CC) and 95% confidence interval (CI) will be presented in the tables.

The secondary BoExp will also be examined to compare the reductions in THS 2.2 vs. SA using the same methodology as above.

TFL number	Title
FIGURES	
15.1.2.1	Urinary MHBMA Quantity Excreted Over 24 hours Mean and 95% CI– FAS
15.1.2.2	Urinary 3-HPMA Quantity Excreted Over 24 hours Mean and 95% CI– FAS
15.1.2.3	Urinary S-PMA Quantity Excreted Over 24 hours Mean and 95% CI– FAS
15.1.2.4	Exhaled CO Arithmetic Mean and 95% CI– FAS
15.1.2.5	1-OHP Urinary Concentration Adjusted for Creatinine Mean and 95% CI– FAS
15.1.2.6	Urinary 1-OHP Quantity excreted Over 24 hours Mean and 95% CI– FAS
15.1.2.7	Total NNN Urinary Concentration Adjusted for Creatinine Mean and 95% CI– FAS
15.1.2.8	Urinary Total NNN Quantity Excreted Over 24 hours Mean and 95% CI– FAS

TFL number	Title
15.1.2.9	4-ABP Urinary Concentration Adjusted for Creatinine Mean and 95% CI- FAS
15.1.2.10	Urinary 4-ABP Quantity Excreted Over 24 hours Mean and 95% CI- FAS
15.1.2.11	1-NA Urinary Concentration Adjusted for Creatinine Mean and 95% CI- FAS
15.1.2.12	Urinary 1-NA Quantity Excreted Over 24 hours Mean and 95% CI- FAS
15.1.2.13	2-NA Urinary Concentration Adjusted for Creatinine Mean and 95% CI- FAS
15.1.2.14	Urinary 2-NA Quantity Excreted Over 24 hours Mean and 95% CI- FAS
15.1.2.15	o-tol Urinary Concentration Adjusted for Creatinine Mean and 95% CI- FAS
15.1.2.16	Urinary o-tol Quantity Excreted Over 24 hours Mean and 95% CI- FAS
15.1.2.17	CEMA Urinary Concentration Adjusted for Creatinine Mean and 95% CI- FAS

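### The CYP1A2 comparison leaves out the Day 0 ratio that the trial already measures, so its confidence intervals will probably be wider than necessary

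*SAP*

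**What the plan says.** Protocol 7.5.2.2 provides that "CYP1A2 activity will be measured at Day 0, and at Day 5". The Day 0 schedule (Protocol Table 9) times the blood sample at "6 hours +/-15minutes after intake of caffeine tablet", and Table 14 repeats this timing on Day 5. On Day 0 all subjects still smoke their own cigarettes, and they learn their arm only on Day 1.

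SAP 12.6.2.4 repeats the schedule: "CYP1A2 activity will be measured in plasma on Day 0 and Day 5". For inference, "The analysis will compare the Day 5 values between the THS 2.2 and CC arms and between the THS 2.2 and SA arms". The model is an ANOVA with sex, daily cigarette consumption and product. It takes over the SAS code of SAP 12.6.1.1, "with no baseline value being included in the model". Day 0 is used only descriptively, for percent change and listings. SAP Section 9, which lists departures from the protocol analysis, does not mention the point.

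**The concern.** A pre-treatment value of the same measurement is usually the most useful covariate available. Here it is collected in all three arms and then left out of the only inferential analysis of an endpoint whose stated objective is to describe changes in CYP1A2 activity.

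Precision is what is at stake. Randomization was stratified by sex and consumption, not by CYP1A2 activity, so chance differences at Day 0 pass into the Day 5 contrast. A one-standard-error imbalance between 80 and 40 subjects is √(1/80 + 1/40) = 0.19 SD. At an assumed correlation of 0.7, about 0.7 × 0.19 = 0.14 SD of that reaches the unadjusted Day 5 difference. The percent-change summaries and the model estimates could then appear to disagree.

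**Working it through.** **1. Is the omission isolated?** Between-arm models in SAP 12.6:

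| SAP section | Endpoint | Baseline in model? |
|---|---|---|
| 12.6.1.1 | Primary biomarkers | Yes: "Model log (Day 5) = log (baseline) sex cigarette_cons product" |
| 12.6.2.1 | Exhaled CO | Yes |
| 12.6.2.1 | Urinary biomarkers | Yes: "An ANCOVA model will be used with terms for the log-transformed baseline value, sex, average daily CC consumption" |
| 12.6.2.2 | Plasma nicotine, cotinine | Yes: "ANCOVA model with terms for baseline (Day 0) concentration, sex, average daily CC consumption over the last 4 weeks" |
| 12.6.2.3 | Nicotine/cotinine PK parameters | No; no Day 0 profile exists |
| **12.6.2.4** | **CYP1A2** | **No, although Day 0 is measured** |
| 12.6.3.1.1 to 12.6.3.1.3 | QSU-brief, MCEQ, MNWS | Yes |
| 12.6.3.2 | Smoking topography | Yes |
| 12.6.3.4 | CYP2A6 | Yes |
| 12.6.3.6 | Risk markers | Yes |

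The PK parameters are the only similar case. They have no baseline because Protocol 7.5.1.2 draws a single nicotine/cotinine sample on Day 0. CYP2A6 is the closest parallel: a plasma metabolic ratio with one Day 0 value, one later value and the same two contrasts. It is baseline-adjusted.

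**2. The plan's own figure.** SAP Section 8 states 80% power, one-sided 2.5%, for a THS 2.2 versus CC difference of 0.631 mL/min/kg (29%) with SD 0.564. With 80 and 40 subjects:

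- SE = 0.564 × √(1/80 + 1/40) = 0.109
- 0.631 / 0.109 = 5.78, and 5.78 − 1.96 = 3.82, so power is about 99.99%

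The stated 80% does not reproduce; it would need an SD of about 1.16. That is a separate matter. Here it means only that power against CC is ample with or without the covariate.

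**3. Effect of adding Day 0.** Let ρ be the Day 0/Day 5 correlation given arm, sex and consumption stratum. It is not in the documents, so a range is assumed. With a large sample the CI width is multiplied by √(1 − ρ²). Allowing for estimation of one more term (residual df 155 without it, 154 with it), the factor is √(1 − ρ²) × √(1 + 1/153) × t₁₅₄/t₁₅₅. A simulation with arms of 80/40/40 and 3,000 trials per value of ρ gave the last column.

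| ρ | √(1 − ρ²) | With df cost | Simulated |
|---|---|---|---|
| 0 | 1.000 | 1.003 | 1.003 |
| 0.3 | 0.954 | 0.957 | 0.957 |
| 0.5 | 0.866 | 0.869 | 0.868 |
| 0.7 | 0.714 | 0.717 | 0.717 |
| 0.8 | 0.600 | 0.602 | 0.603 |

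The break-even point is |ρ| of about 0.08. Both estimators were unbiased in the simulation: mean estimates ran from −0.627 to −0.632 against a true −0.631. A further simulation of 4,000 trials per value gave the same narrowing for THS 2.2 versus SA, which also compares 80 with 40 subjects.

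**4. Illustration in units.** No SD is given for the paraxanthine/caffeine ratio, so the caffeine-clearance SD of 0.564 stands in. The half-width without Day 0 is 1.975 × 0.109 = 0.216. The implied CC mean is 0.631 / 0.29 = 2.18.

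| ρ | Half-width | Share of CC mean |
|---|---|---|
| no Day 0 term | 0.216 | 9.9% |
| 0.3 | 0.206 | 9.5% |
| 0.5 | 0.187 | 8.6% |
| 0.7 | 0.155 | 7.1% |
| 0.8 | 0.130 | 6.0% |

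**5. Missing Day 0 ratios.** SAP 7.1.4 calculates no ratio when either concentration is below quantification, and SAP 12.1.5 generally does not impute. If a share f of subjects lacks Day 0, the variance changes by about (1 − ρ²)/(1 − f). The covariate therefore still helps unless f exceeds ρ²: 9%, 25%, 49% and 64% for the four correlations.

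**The case against.** The case for leaving the plan alone is reasonable. The contrast is unbiased, the objective is descriptive, and CYP1A2 is outside the success criterion. Nothing contradicts the protocol, which specifies baseline adjustment for the biomarkers of exposure, and CYP1A2 is not one of them. The size of the gain rests on an assumed correlation, which need not be equal across arms, and the illustration uses clearance rather than the analysed ratio. Adding Day 0 can cost subjects. The SA comparison is already planned in the text.

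Most of this limits the importance of the point without removing it. The gain is conditional on ρ, but the condition is weak: |ρ| above about 0.08 for repeated measurement of one enzyme ratio in the same person, against a 0.3% loss if ρ is zero. The relative narrowing does not depend on the clearance scale; only the half-widths in units do. Loss of subjects reverses the gain only above the shares shown.

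Two qualifications stand. The narrowing is the same for both contrasts; it is more useful for SA only because the SAP states no CYP1A2 power or precision there. And the claim that other models adjust for baseline covers those specified in SAP 12.6. Section 9 also announces product-by-time models for COHb and exhaled CO without listing baseline terms.

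**Conclusion.** The concern holds. SAP 12.6.2.4 leaves out a scheduled baseline without a reason, against the SAP's own practice elsewhere. The result stays valid, but the interval is likely to be wider than it needs to be: about 4%, 15%, 40% or 66% wider at correlations of 0.3, 0.5, 0.7 or 0.8 (the reciprocals of the factors above). These figures assume a common linear Day 0/Day 5 relation in all arms and nearly complete Day 0 data. The change should be made because it is cheap. No study conclusion depends on it.

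A smaller ambiguity belongs with it. The borrowed code logs the Day 5 value and asks only for comparisons with CC, while 12.6.2.4 reports a difference and also wants THS 2.2 versus SA. Other sections that reuse the code share this.

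**What to change.** In SAP 12.6.2.4, replace the ANOVA by an ANCOVA with the Day 0 CYP1A2 ratio, sex, cigarette-consumption stratum and product.

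- State the scale before unblinding and put response and covariate on the same one: both logged and reported as geometric mean ratios, or both untransformed and reported as differences.
- Write the code so that it returns both THS 2.2 versus CC and THS 2.2 versus SA.
- Report how many subjects are left out because no Day 0 ratio could be calculated.

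The cost is one covariate and one contrast statement. The Day 0 caffeine test is already scheduled in every arm. If the omission was deliberate, the SAP should give the reason.
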